**Table 2 - Data Documentation Schedule** 

Assessment/ Procedure		Treatment Period		Post-treatment (PT) Period			
(only available data to be collected; no diagnostic or monitoring procedures to be applied to the patients apart from those of routine clinical practice)	Baselin	On- treatment visits	Mid treatment visit for pts receiving 24 weeks of therapy	EoT b	Early PT visit	SVR 12 visit	SVR 24 visit
Patient authorization	X a						
Demographic information	Χ						
IL28B	Χ						
Relevant CHC disease characteristics	Х						
Liver fibrosis stage	Х						
CHC treatment history	Χ						
HCV genotype and subtype	Χ						
HCV RNA samples	Х	Х	Х	Х	Х	Χ	Χ
Clinical chemistry and hematology	Χ	Х	Χ	Х	Х	Х	Х
ABBVIE REGIMEN initiation documentation	Х						
ABBVIE REGIMEN adherence		Х	Χ	Х			
Concomitant medication	Χ	Х	Χ	Χ			
Relevant medical history, co-morbidities	Χ						
sAE, AE and pregnancy reporting	Х	Х	Х	Х	Xc	$X_q$	Xd
For patients receiving RBV: Evidence, in accordance with local label, that female patient or female partner of male patient is not pregnant	Х						
Patient questionnaires – WPAI, EQ5D-5L	Χ			Х		X	Х

Abbreviations: EoT = End of Treatment (at Week 12 or 24 or at premature discontinuation), PT = Post-Treatment

- a Written patient authorization must be obtained before any data documentation in the eCRF
- b Patients who prematurely discontinue should return to the site to document EoT data
- c Tolerability documentation until PT week 4
- d Pregnancy reporting for patients treated with DAA plus RBV

In accordance with the non-interventional nature of the study all HCV RNA measurements will be performed at the sole discretion of the physician and all HCV RNA measurements have to be entered into the eCRF. All recorded HCV RNA values will be assigned to appropriate time points (baseline, on-treatment visits, EoT visit, post-treatment visits) as follows:

Table 3 - Analysis Time Windows for HCV RNA

Phase	Time point	Time Window
Pre-Treatment	Baseline	Last value prior to start of study treatment (i.e.
		≤study day 1)
On-treatment		Study day during treatment period^#
		(Study day 1 = first treatment day)
Treatment Week	4 (RVR*)	15 - 42^
EoT	Actual EoT	Study day of last dose#
		(28 days prior to last dose - 7 days post last
		dose)
Post Treatment	12 weeks (SVR 12	>=70-126 days post last dose
	window)	
	24 weeks (SVR24	127-210 days post last dose
	window)	

^values must also be <= 7 days post last dose

#>=study day 2

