# 4.2.5 Patient Disposition

The frequencies of patients belonging to the different populations (i.e. EP, TP, CP, CPSFU; SP) will be summarized by genotype and cirrhosis status and overall using the EP analysis groups as specified in section 4.2.1. The reasons for exclusion from a particular population will be also summarized in the frequency tables. Additionally, information on patient disposition will be listed.

Furthermore the frequency of patients not completing the study as defined per protocol (i.e. no HCV RNA assessment performed at least 10 weeks post-treatment), will be summarized by treatment regimen and cirrhosis status and additionally by genotype and cirrhosis status and overall for the SP and CP. The reasons for not completing the study as entered on the CRF will be displayed (i.e. failure to return, insufficient virological response (HCV RNA detectable at End of treatment, Relapse post-treatment), patient never started treatment, withdrawn consent, death, other).

Additionally, the main reason for early termination of the ABBVIE regimen (AE or SAE [Physician decision], virological non-response [Physician decision], rebound or breakthrough [Physician decision], resistance to DAA [Physician decision], patient refused to continue treatment, patient withdrew consent to participate in the study, lost to follow-up, other, unknown [if actual duration is shortened for more than 7 days]) and Ribavirin (Anemia, Nausea/Vomiting, Rash, Other) will be summarized by treatment regimen and cirrhosis status and additionally by genotype and cirrhosis status and overall for the following different analysis populations: CP and SP.

Finally the study regimens assigned at baseline will be summarized (a) by genotype and cirrhosis status and (b) by genotype and pre-treatment status (treatment naïve vs treatment experienced) for CP and SP.

An overview of Tables is given in Table 6.

Table 6 Overview of Outputs for Patient Disposition

Output Title	Output Short Name	Analysis Population
Patient Disposition by Genotype and Cirrhosis Status – EP - <country></country>	tdis_ <c>_gc_ep</c>	Patients Enrolled
Listing of Patient Disposition - EP- <country></country>	ldis_ <c>_ep</c>	Patients Enrolled
Premature Termination of the Study and its Main Reason by <treatment genotype="" regimen=""> and Cirrhosis Status - CP - <country></country></treatment>	tps_ <c>_<t g="">c _cp</t></c>	Core population

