# 4.2.7.2 Secondary Variables

# 4.2.7.2.1 Secondary Effectiveness Variables

#### Response

For the other response rates (i.e. RVR, SVR24, EoT response rate, relapse rate, viral breakthrough), the simple percentage of patients and a two-sided 95% confidence interval (CI) of the percentage will be computed (based on the Wilson's score method) as well. The RVR and EoT response rates will be reported for CP and the SVR24 rate will be reported for the respective CPSFU, stratified by genotype and cirrhosis status and overall. The relapse rates will be estimated stratified by SVR window (i.e. during SVR12 window=relapse12, during SVR24

window=relapse24) and stratified by genotype and cirrhosis status and overall in patients of the CP with EoT response who fulfilled the following criteria:

- completed treatment as defined previously.
- had at least one HCV RNA measurement >= 70 days post-treatment or was a treatment failure between EoT and 70 days post-treatment.

Viral breakthrough rates [defined as at least one documented HCV RNA <50 IU/mL followed by HCV RNA ≥50 IU/mL during treatment] will be estimated overall and stratified by genotype and cirrhosis status in all patients of the CP, who have at least one undetectable or unquantifiable, ontreatment HCV RNA measurement and at least one on-treatment or EoT measurement thereafter.

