#### Non-Response

In another table, the numbers and the percentages of the SVR12 non-responder categories and responder will be summarized for CP patients, overall and stratified by genotype and cirrhosis status. The following SVR12 non-response categories will be considered:

- On-treatment virologic failure (breakthrough [defined as at least one documented HCV RNA <50 IU/mL followed by HCV RNA ≥50 IU/mL during treatment] or failure to suppress [each measured on-treatment HCV RNA value ≥50 IU/mL])
- Relapse (defined as HCV RNA <50 IU/mL at EoT or at the last on-treatment HCV RNA measurement followed by HCV RNA ≥50 IU/mL post-treatment and completed treatment as defined previously)
- Death and none of the above
- Premature study drug discontinuation with no on-treatment virologic failure and none of the above
- Insufficient virological response, other than those mentioned above (patients for whom
  insufficient virological response was reported, or who had HCV RNA >=50 IU/mL post
  EoT and no HCV RNA test on treatment) and none of the above
- Missing SVR12 data and/or none of the above criteria

Virological response rates and non-response categories will be displayed for patients who completed treatment with AbbVie regimen, as well.

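### The relapse numerators cover only days 70-126 and 127-210, although failures before day 70 are in the denominator; read literally, the windowed relapse rates are biased low

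*SAP*

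**What the plan says.** SAP 4.1.2 defines relapse as HCV RNA below 50 IU/mL at EoT followed by a value of 50 IU/mL or more. It sets no time limit and asks for no confirmatory test.

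SAP 4.2.7.2.1 (Response) then splits the rate: "The relapse rates will be estimated stratified by SVR window (i.e. during SVR12" window (relapse12) and during the SVR24 window (relapse24). The denominator is CP patients with EoT response who completed treatment and who "had at least one HCV RNA measurement >= 70 days post-treatment or was a treatment failure between EoT and 70 days post-treatment".

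The windows are in SAP 4.2.2, Table 3:
- EoT: "28 days prior to last dose - 7 days post last" dose
- SVR12: ">=70-126 days post last dose"
- SVR24: "127-210 days post last dose"

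In the SVR12 non-response table (SAP 4.2.7.2.1, Non-Response), relapse again has no window: response at EoT or at the last on-treatment test, "followed by HCV RNA ≥50 IU/mL post-treatment and completed treatment".

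Protocol 9.7.3.3 does not split relapse by window.

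**The concern.** The denominator and the numerators do not match. The denominator goes out of its way to include patients who failed before day 70, while neither numerator reaches back before day 70. A programmer who applies Table 3 as written would keep an early relapser in the denominator and count that patient as relapse-free in both rates.

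The plan allows for such patients in three places:
- The documentation schedule (SAP Table 2) has HCV RNA at an early post-treatment visit.
- SAP 4.2.5 lists, among the reasons for having no HCV RNA test at 10 weeks (70 days) or later, "insufficient virological response (HCV RNA detectable at End of treatment, Relapse post-treatment").
- SAP 4.2.3 excludes HCV RNA values from the start of any other HCV treatment. An early relapser who starts another treatment before day 70 therefore has no usable value in either window, even if tested.

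Relapse is a named secondary effectiveness endpoint, and the error can only lower it.

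**Working it through.** The documents give no expected relapse rate or precision, so there is no figure of the plan's to reproduce. The check has two parts.

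**1. Coverage of the windows.** The EoT window ends on day 7 after the last dose, and the SVR12 window starts on day 70. Days 8-69 belong to no relapse stratum. That is 69 - 8 + 1 = 62 of the 210 - 8 + 1 = 203 days from the end of the EoT window to the end of the SVR24 window.

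Applying the rules to test patients, all completers with EoT response:

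| Post-treatment HCV RNA | In denominator | relapse12 | relapse24 | Relapse under 4.1.2 |
|---|---|---|---|---|
| Positive on day 8, 28 or 69 only, no later test | yes | no | no | yes |
| Positive on day 28 and again on day 84 | yes | yes | no | yes |
| Positive on day 84 | yes | yes | no | yes |
| Negative on day 84, positive on day 168 | yes | no | yes | yes |
| First positive on day 220, no other test | yes | no | no | yes |
| Negative on day 84, no later test | yes | no | no | no |

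Row 1 is the gap. Row 2 shows that it closes if the patient has a usable positive retest in a window. Row 5 shows a second, smaller gap after day 210.

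**2. Illustrative size.** If a share s of relapses is seen only on days 8-69, the two windows together report the true rate × (1 - s). Assumptions: 360 patients in the denominator, borrowed from the lower end of the evaluable CP range in SAP 3.2 (the relapse denominator would be smaller), and 12 relapses. Intervals are 95% Wilson score, the SAP's method: [p + z²/2n ± z√(p(1-p)/n + z²/4n²)] / (1 + z²/n), with z = 1.96.

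| Seen only on days 8-69 | Reported | Rate | 95% interval |
|---|---|---|---|
| 0 of 12 | 12/360 | 3.33% | 1.92-5.74 |
| 3 of 12 | 9/360 | 2.50% | 1.32-4.68 |
| 6 of 12 | 6/360 | 1.67% | 0.77-3.59 |
| 9 of 12 | 3/360 | 0.83% | 0.28-2.42 |

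With 4 relapses (1.11%), of which 1 to 3 are seen only early, the reported rate is 3/360 = 0.83% down to 1/360 = 0.28%. With 18 relapses (5.00%), of which 4 to 14 are seen only early, it is 14/360 = 3.89% down to 4/360 = 1.11%.

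**The case against.** The strongest reply is that early failures were meant to count. Admitting a patient who "was a treatment failure between EoT and 70 days post-treatment" has little purpose otherwise, and the window labels could be shorthand for relapse status at the SVR12 assessment. SAP 4.2.3 can be read in support. It treats a patient with no value in the analysis window, after imputation, as a failure. Within this denominator, a patient tested on days 70-126 has an SVR12 value and one tested only later has a value carried back, so the patients left without one are the early failures.

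The point about intent stands: a reader might infer that the plan deliberately discards early relapses, and the documents do not support that. The appeal to 4.2.3 does not settle the matter. That rule is written for RVR, EoT response and SVR and does not name relapse. Extended to relapse24, it would label an SVR12 responder with no later test a relapser, which cannot be intended. The literal text therefore still leaves early failures out.

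It is also fair that the table shells (SAP Part II) are not among the documents, so an early or total relapse row there cannot be ruled out. Completers with an early relapse still appear as relapse in the non-response table, so their failure is not hidden from the report.

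**Conclusion.** The point holds as a mismatch in the written rule. Followed literally, the rule biases relapse12 and relapse24 taken together low by the share of relapses seen only on days 8-69 without a usable positive retest. That share is not in the documents and may be zero. The percentages above rest on assumed counts and are not a forecast.

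Two stronger readings are not supported. A reader might infer that the primary result is affected. It is not: a patient with no SVR12 value after imputation counts as an SVR12 failure. A reader might also infer that the relapse table and the non-response table ought to agree, and that any difference would reveal this gap. They differ by design. The non-response table covers SVR12 non-responders only, so a patient negative on day 84 and positive on day 168 is not a relapse there. It also accepts response at the last on-treatment test, and it takes percentages of CP patients rather than of the restricted relapse denominator.

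This should be corrected before the analysis, because a named secondary endpoint would otherwise be computed inconsistently with its own definition.

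**What to change.** In SAP 4.2.7.2.1, state that:
- relapse12 counts any HCV RNA of 50 IU/mL or more from day 8 (after the EoT window) through day 126 after the last dose, in an EoT responder who completed treatment;
- relapse24 counts a first HCV RNA of 50 IU/mL or more on days 127-210 in a patient without relapse12.

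Add one overall relapse row using the 4.1.2 definition without a window. It also captures first positives after day 210. Do not require this row to equal the relapse line of the non-response table; footnote the differences in population, definition and denominator. Because 4.1.2 asks for no confirmatory test, an isolated positive on days 8-69 followed by a negative in the SVR12 window would count both as relapse12 and as SVR12 response. The footnote should say so.

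The cost is two sentences, one table row and one footnote. No new data are needed.

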#### Non-Response

In another table, the numbers and the percentages of the SVR12 non-responder categories and responder will be summarized for CP patients, overall and stratified by genotype and cirrhosis status. The following SVR12 non-response categories will be considered:

- On-treatment virologic failure (breakthrough [defined as at least one documented HCV RNA <50 IU/mL followed by HCV RNA ≥50 IU/mL during treatment] or failure to suppress [each measured on-treatment HCV RNA value ≥50 IU/mL])
- Relapse (defined as HCV RNA <50 IU/mL at EoT or at the last on-treatment HCV RNA measurement followed by HCV RNA ≥50 IU/mL post-treatment and completed treatment as defined previously)
- Death and none of the above
- Premature study drug discontinuation with no on-treatment virologic failure and none of the above
- Insufficient virological response, other than those mentioned above (patients for whom
  insufficient virological response was reported, or who had HCV RNA >=50 IU/mL post
  EoT and no HCV RNA test on treatment) and none of the above
- Missing SVR12 data and/or none of the above criteria

Virological response rates and non-response categories will be displayed for patients who completed treatment with AbbVie regimen, as well.

#### **SVR24 (Exploratory Analyses)**

Univariate and multiple logistic regression (MLR) methods will be used to investigate the impact of various explanatory covariates (patient and disease characteristics) at baseline on SVR24.

These analyses will be of exploratory nature, data driven, and will be performed for CP population. Univariate logistic regression will be performed first and then backward selection procedures will be applied to generate the final MLR model. A p-value <0.05 will be used for the covariates to stay in the model in a backward elimination step. If the percentage of patients with available data for a variable is lower than 80% of the patient group analyzed, then this variable will not be considered in the MLR analysis.

The variables to be considered are as follows:

- · Key demographic information
  - o Age (continuous)
  - o Gender (Female [reference], Male)
  - Race/ethnic origin (White/Caucasian [reference], Black, Asian/Oriental, Other [all other races]); at least two categories with at least 10% of the patients each have to exists, so that this variable will be considered
  - Weight (continuous)
  - o BMI (continuous)
  - IL28B, rs12979860 (CC [reference], CT or TT); patients with unknown genotype are excluded from the respective analyses.
- CHC disease characteristics
  - Years since diagnosis (continuous)
  - Mode of CHC infection (Drug use [reference], Other [all other answers excluding unknown], unknown);
  - Most recent stage of liver fibrosis (No cirrhosis/Transition to cirrhosis [reference],
     Cirrhosis; for definition see 4.2.6.2);
- HCV RNA level at baseline (log10 IU/mL)
- HCV genotype( G1a\*, G1b, G4; for definition see section 4.2.6.2)
- Type of treating institute (Private Practice / Private Hospital, Academic / University Hospital, General Hospital, Other)
- Co-infections (every patient not reporting the respective co-infection is considered as not having the respective co-infection)
  - o HIV(No [reference], Yes)
  - HBV(No [reference], Yes)
- Liver and/or CHC related co-morbidities (every patient not reporting the respective co-morbidity is considered as not having the respective co-morbidity)
  - o Liver transplantation (No [reference], Yes)
  - Steatosis (non-alcoholic) (No [reference], Yes)
  - o Decompensated liver disease (No [reference], Yes)
- Other co-morbidities (every patient not reporting the respective co-morbidity is considered as not having the respective co-morbidity)
  - o Depression (No [reference], Yes)

- Diabetes mellitus (No [reference], Type 1/Type 2)
- Hypertension (No [reference], Yes)
- Immunologically mediated disease (No [reference], Yes)
- Hypothyroidism (No [reference], Yes)
- Alcohol use (None [reference], Yes –occasional, Yes –regular, Exdrinker)
- Key clinical chemistry and hematology laboratory variables at baseline
  - o ALT ratio (continuous, see 4.2.6.5)
  - o AST ratio (continuous, see 4.2.6.5)
  - Platelets [10^9/L] (continuous)
- Prior treatment status (HCV treatment naïve [reference], HCV treatment experienced)

Additionally, an interaction term for cirrhosis status and genotype will be considered. If the most recent stage of liver fibrosis status (No cirrhosis/Transition to cirrhosis vs Cirrhosis), the genotype (G4, G1b vs G1a) or the interaction of both remains in the final model, then additional MLR might be considered for the subgroups concerned, taking into account the treatment regimen (e.g. in cirrhotic G1 patients: RBV vs no RBV and 12 wks vs 24 weeks).

The categories pre-specified above could be modified in the analyses if this is supported by the data (e.g. categories could be combined, if their impact on SVR24 is similar). Furthermore, continuous variables can be replaced by categorical variables.

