9.7.3.3 Statistical Methods for Analysis of Effectiveness Variables

The simple percentage of patients achieving SVR12 will be calculated and an exact two-sided 95% confidence interval (CI) of the percentage will be computed based on the Clopper-Pearson method.

Corresponding methods will be used for other response rates (EoT response rate, relapse rate, viral breakthrough). The relapse rates will be estimated in patients of the CP analysis groups with EoT response and sufficient HCV RNA measurements post-treatment. Viral breakthrough rates will be estimated in all patients of the CP analysis groups, who have at least one undetectable HCV RNA measurement on-treatment and at least one on-treatment or EoT measurement thereafter.

Univariate and multiple logistic regression (MLR) methods will be used to investigate the impact of the following explanatory covariates on SVR12:

- Key demographic information
- Mode of CHC infection
- HCV RNA level at baseline
- Most recent stage of liver fibrosis
- HCV genotype and subtype (if available)
- Type of treating institute
- Liver and/or CHC related co-morbidities
- Key clinical chemistry and hematology laboratory variables at baseline
- In treatment experienced patients only:
 - Most recent prior treatment for CHC
 - Outcome of most recent prior CHC treatment

Further details and additional covariates will be specified in the SAP.

These analyses will be of exploratory nature, data driven, and will be repeatedly performed for various CP Analysis Groups, since not each covariate might be

predictive in each patient group. Furthermore, the fact that treatment regimens will differ in the various patient groups has to be taken into account, when selecting the patient groups for each MLR analysis. Backward selection procedures will be applied to generate the final MLR models which consider only covariates in the selection procedure with a p-value <0.25 in the corresponding univariate logistic regression analysis. A p-value <0.05 will be used for the covariates to stay in the model in a backward elimination step. Logistic regression methods will also be used to investigate the impact of treatment adherence on SVR12.

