# 4.2.3 Handling of missing data

No data will be imputed for any effectiveness or safety analyses except for the analyses of the HCV RNA endpoints and certain PRO endpoints. The discussion of missing data imputation for the PRO endpoints is included in section 4.2.7.2.3.

HCV RNA values will be selected for an RVR, EOTR and SVR analysis based on visit windows as defined in Table 3. When there is no HCV RNA value in a visit window based on defined visit windows, the closest values before and after the window, regardless of the value chosen for the subsequent and preceding window, will be used for the flanking imputation described below. For analysis of RVR, EOT and SVR, if a subject has a missing HCV RNA value at a post-Day 1 visit but with undetectable or unquantifiable (≤50 IU/mL) HCV RNA levels at both the preceding value and succeeding value, the HCV RNA level will be considered undetectable or unquantifiable,

respectively, at this visit for this subject. In addition, if a subject has an unquantifiable HCV RNA level at the preceding value and an undetectable HCV RNA level at the succeeding value, or vice versa, the HCV RNA level will be imputed as unquantifiable at this visit for this subject.

For analyses of RVR, subjects still missing a value for the visit after flanking imputation will be imputed as a failure. For EoTR and SVR analysis, if there is no value in the appropriate window after flanking imputation but there is an HCV RNA value after the window, then it will be imputed into the EoTR or SVR window respectively. Subsequent to this flanking imputation, if a subject is missing a value for the visit window associated with the analysis, the subject will be imputed as a visit failure (i.e., not undetectable or unquantifiable).

If a subject starts another treatment for HCV, then all HCV RNA values for this subject measured on or after the start date of the new HCV treatment will be excluded from analyses. The subject will be considered a failure for summaries of viral response at all time points after the start of the new HCV treatment.

Due to the non-interventional nature of this study several different methods for determination of the HCV RNA value can be applied. For the purpose of the statistical analysis, a HCV RNA measurement is considered ≤50 IU/mL.

- if a PCR test was used

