In addition to the summary statistics of the adherence variables, logistic regression analyses will be performed for the following adherence variables: "adherence to Abbvie regimen" in all patients of the CP, "adherence to ribavirin" in all patients of the CP taking RBV, each categorized as follows: >=95%, >80%-<=95%, <=80% to investigate the additional impact of overall treatment adherence on SVR24. The categories may be changed if they are sparsely filled. Adherence will be included as mandatory covariate in addition to the baseline explanatory variables already mentioned above. Also the same methods will be applied as described above.

An overview of Tables is given in Table 8.

Table 8 Overview of Outputs for Primary and Secondary Effectiveness Analysis

Output Title	Output Short Name	Analysis Population
Virological Response Rates by Genotype and Cirrhosis Status – CP/CPSFU - <country></country>	tvr_ <c>_gc_cp</c>	Core population/ Core population with sufficient follow-up data
Virological Response Rates by Genotype and Cirrhosis Status in Patients who Completed ABBVIE Regimen – CP/CPSFU - <country></country>	tvr_ <c>_gc_cp_ARC</c>	Core population/ Core population with sufficient follow-up data: patients who completed ABBVIE regimen
Virological Response Rates - NCP - <country></country>	tvr_ <c>_ncp</c>	Non-core population
Relapse Rates by Genotype and Cirrhosis Status – CP - <country></country>	trr_ <c>_gc_cp</c>	Core population
Viral Breakthrough by Genotype and Cirrhosis Status – CP - <country></country>	tvb_ <c>_gc_cp</c>	Core population
Non-Response Rates by Genotype and Cirrhosis Status – CP - <country></country>	tnrr_ <c>_gc_cp</c>	Core population
Non-Response Rates by Genotype and Cirrhosis Status in Patients who Completed ABBVIE Regimen – CP - <country></country>	tnrr_ <c>_gc_cp_ARC</c>	Core population: patients who completed ABBVIE regimen
Impact of Patient and Disease Characteristics on SVR24 – CP - <country></country>	tis_ <c>_cp</c>	Core population
Adherence by Genotype and Cirrhosis Status - CP - < country>	tah_ <c>_gc_cp</c>	Core population
Adherence by Treatment Regimen and Cirrhosis Status - SP - <country></country>	tah_ <c>_gc_sp</c>	Safety population
Impact of Adherence to AbbVie Regimen on SVR24 - CP - <country></country>	tiaa_ <c>_cp</c>	Core population
Impact of Adherence to Ribavirin on SVR24 in patients taking RBV – CP - <country></country>	tiar_ <c>_cp_RBV</c>	Core population: patients taking RBV

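### The SAP moves the predictor and adherence regressions from SVR12 to SVR24 in the core population without declaring the change, so documented SVR12 responders with no later test are modelled as failures

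*SAP*

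**What the plan says.** **Protocol.** Section 9.7.3.3 states: "Univariate and multiple logistic regression (MLR) methods will be used to investigate the impact of the following explanatory covariates on SVR12". For adherence it adds: "Logistic regression methods will also be used to investigate the impact of treatment adherence on SVR12". The covariate models "will be repeatedly performed for various CP Analysis Groups". The abstract names the same outcome. Protocol 9.7.1 and 9.7.3.1 define SVR12 by the single last HCV RNA value at least 70 days after the last dose, with no upper limit.

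**SAP.** Section 4.2.7.2.1, under its SVR24 heading, changes the outcome: "methods will be used to investigate the impact of various explanatory covariates (patient and disease characteristics) at baseline on SVR24". The population follows: "These analyses will be of exploratory nature, data driven, and will be performed for CP population". The adherence models are fitted "to investigate the additional impact of overall treatment adherence on SVR24". Three outputs in Table 8 carry SVR24 in their titles: "Impact of Patient and Disease Characteristics on SVR24" and the two adherence-impact tables. No regression on SVR12 remains.

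**Coding of missing values.** SAP Table 3 sets the SVR24 window at days 127-210. In SAP 4.2.3, flanking imputation needs a response on both sides of the empty window, and the carry-back step needs a value after it. Otherwise, "if a subject is missing a value for the visit window associated with the analysis, the subject will be imputed as a visit failure".

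**Contrast within the SAP.** The SVR24 rate itself is reported in CPSFU24 (4.2.7.2.1, Response). That population leaves out responders whose later test is missing for reasons unrelated to safety or effectiveness (4.2.1).

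**The concern.** Secondary objectives 2 (predictive factors) and 4 (adherence) rest on these models. The SAP identifies two other departures from the protocol: the 126-day upper limit for SVR12 (4.1.1) and the replacement of the laboratory shift tables (4.2.8.4). It does not identify this one and gives no reason for it.

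The change matters because few true failures are expected. A patient with a documented response at week 12 who is not tested again is a success in the primary analysis and has completed the study as SAP 4.2.5 defines it (an HCV RNA assessment at least 10 weeks post-treatment). In the regression the same patient is a failure. With so few real non-responders, a modest number of such patients can weaken true predictors. If missed tests are related to a covariate, they can also create an apparent predictor. Adherence is an obvious candidate, since poor adherers might also skip a late test, although nothing in the documents shows that they do.

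**Working it through.** **1. The plan's own figures.** Clopper-Pearson limits at n=360 give a width of 6.47% at 90% SVR12 and 4.80% at 95%. Protocol Table 3 and SAP Table 1 state 6.5% and 4.8%, so the planning inputs reproduce. They imply 360 × 0.05 = 18 or 360 × 0.10 = 36 SVR12 non-responders.

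**2. The coding rule applied to test patients** (days after last dose; all values are responses).

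| HCV RNA values | SVR24 under SAP 4.2.3 |
|---|---|
| EoT, day 84 | failure |
| EoT, day 126 | failure |
| EoT, days 84 and 168 | success |
| EoT, days 84 and 230 | success (carried back) |

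The exact condition for a missing-only failure is therefore no value after day 126.

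**3. Added failures.** Let s be the SVR12 rate in the CP and q the share of SVR12 responders with no value after day 126. The documents give no q, so it is an assumption. Added failures = 360·s·q, and their share of modelled failures = s·q / [(1−s) + s·q]. For s=0.95 and q=0.05: 360 × 0.95 × 0.05 = 17.1, and 0.0475 / 0.0975 = 49%.

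| q | Added, s=95% / 90% | Share of failures, s=95% / 90% |
|---|---|---|
| 2% | 7 / 6 | 28% / 15% |
| 5% | 17 / 16 | 49% / 31% |
| 10% | 34 / 32 | 66% / 47% |

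Added failures outnumber SVR12 non-responders once q exceeds (1−s)/s, which is 5.3% / 11.1%.

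**4. Dilution when q is the same in both groups.** Take two equal groups with an odds ratio (OR) of 3.0 for SVR12 failure: 7.4% vs 2.6% (mean 5%), or 14.6% vs 5.4% (mean 10%). Observed failure is p + (1−p)q. At s=95% and q=5% this gives 12.0% vs 7.5%, so the OR is 1.70. For q = 2, 5, 10% the OR is 2.14, 1.70, 1.42 (s=95%) and 2.48, 2.07, 1.73 (s=90%).

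**5. Spurious effect when q differs by covariate.** Take equal SVR12 in both groups and failure (1−s) + s·q in each.

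| q in the two groups | OR, s=95% / 90% |
|---|---|
| 2% vs 1% | 1.17 / 1.09 |
| 5% vs 2% | 1.46 / 1.27 |
| 10% vs 5% | 1.57 / 1.38 |

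**6. How much is due to the switch.** Suppose 10% vs 5% counts all virological responders untested after day 126, and a fraction f of them has no value from day 70 either. SVR12 in the CP then fails those patients too. Its OR is 1.00, 1.36, 1.57 (s=95%) or 1.00, 1.21, 1.38 (s=90%) for f = 0, 0.5, 1, against 1.57 / 1.38 under SVR24. The step 5 figures are attributable to the switch in full only at f = 0.

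**7. Residual bias in a CPSFU fit.** Dropping untested responders leaves failure odds (1−s)/[s(1−q)], so the spurious OR is (1−q0)/(1−q1): 0.98/0.95 = 1.03 for 5% vs 2%, and 0.95/0.90 = 1.06 for 10% vs 5%.

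**The case against.** **Points that stand.** Every magnitude rests on an assumed q, which may be low. Both documentation schedules include an SVR24 visit with HCV RNA, follow-up is planned to 24 weeks, the window is 84 days wide, and a later value is carried back. Testing is nevertheless at the physician's discretion. Dilution needs only some missed tests. A spurious effect also needs missingness that differs by covariate, which the documents do not show, and at 2% vs 1% it is negligible. Missing-as-failure is the protocol's own rule (9.7.1), and Protocol 9.9 already concedes that missing HCV RNA lowers the estimated SVR rate. SVR24 captures late relapse, which the SAP's 70-126-day SVR12 does not. The protocol's SVR12, however, takes the last value from day 70 on and captures it too.

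**Points that do not remove the concern.** SVR24 is named openly in the heading and output titles, and objectives 2 and 4 do not name SVR12. But Protocol 9.7.3.3 does name it, and its allowance for further details and additional covariates does not extend to a different outcome.

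**Stronger readings the documents do not support.**
- A reader might infer that using the CP is itself a departure. It is not: the total CP is one of the SAP's CP analysis groups (4.2.1), and subgroup models remain possible.
- A reader might infer that the interim analysis cuts off SVR24 follow-up. The last eligible starter (31 March 2016, 12-week regimen, last dose 22 June 2016) reaches week 24 on 7 December 2016. With an assumed cut on 31 December, that patient loses only days 193-210, which is 18 of 84 window days, all beyond the planned 168 days of observation.

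**Conclusion.** The departure is real and follows from the text alone: a different outcome for both sets of regressions, not identified as a change and not justified. The coding of documented SVR12 responders as failures also follows from the text and needs no assumed figure. It conflicts with the primary analysis and with the SAP's own choice of CPSFU24 for the SVR24 rate.

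The size depends on a missed-test share that the documents do not give. If it is near zero, the numerical effect is small and only the undeclared change remains. At an assumed 5% of responders, about half (95% SVR12) or a third (90% SVR12) of modelled failures would be missing data only, and an OR of 3.0 would read as about 1.7 or 2.1.

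A reader might go further and infer that the study's effectiveness results are biased. The documents do not support that: the regressions are labelled exploratory, and neither the primary SVR12 estimate nor the SVR24 rate in CPSFU24 is affected. The point should be fixed, in proportion to analyses of secondary, exploratory standing.

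**What to change.** In SAP 4.2.7.2.1 and the three regression outputs of Table 8:

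- Restore the protocol's outcome, SVR12 as the single last HCV RNA value at 70 days or later, in the CP. Say in the text that this differs from the 70-126-day window of the primary analysis and also captures late relapse.
- Add a CPSFU12 fit as a sensitivity analysis, as SAP 4.2.7.1 does for the primary endpoint.
- If SVR24 models are kept, declare and justify the departure and fit them in CPSFU24, with the CP missing-as-failure version as the sensitivity analysis.
- In each table, report how many modelled failures are due to missing data only.

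The cost is SAP wording, three table titles and slightly more analysis work, with no new data. Some limits remain. SVR12 in the CP still fails patients untested from day 70. CPSFU drops untested responders, which leaves the residual OR of about 1.03-1.06 in the 5% vs 2% and 10% vs 5% scenarios. With 27 candidate covariates plus an interaction and about 18-36 events, the models stay fragile under any outcome.
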